11.2 Derived and transformed data

Baseline will be considered to be the latest value obtained before study drug administration (eg Day 1, pre-dose; or Day -1 if not recorded at pre-dose; or screening if not recorded at pre-dose or on Day -1).

Laboratory data will be reported in standard units. Out-of-range laboratory tests may be repeated. If a test is out of-range at baseline and repeated before dosing, the latest repeat value before dosing will be used as baseline. However, if a test is out-of-range and repeated at any other time during the study, the out-of-range value (not the repeat value) will be included in statistical summaries.

TriPLICATE vital sign measurements will be made at screening and the mean of the three measurements for each subject will be used for analysis.

The PK parameters to be derived are given in Appendix A: Pharmacokinetic Analysis.

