11.1 Premature withdrawal and missing data

All subjects who withdraw prematurely from the study or study drug will be included in the statistical analyses.

If a subject completes the treatment period but has missing data, then this will be made apparent in the subject listings. Missing data will not be imputed except for as outlined in Section 11.2.

If the study is prematurely discontinued, all available data will be listed and a review will be carried out to assess which statistical analyses are still considered appropriate.

Data collected at unscheduled time points during the study will not be used in the summaries or data analyses. They will be included in the listings.

If time information (ie hours and/or minutes) for adverse events (AEs) or concomitant medication is missing, but the day is present, then the time will be calculated in days. If date information is partial or missing, then any derived times (eg AE start time from last study medication) will be listed as missing.

Conventions for handling missing plasma concentrations are given in Appendix A: Pharmacokinetic Analysis.

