14.3 SAFETY DATA				
14.3.1.1	Summary of treatment-emergent adverse events	Safety	16.2.7.1	T_AE1
14.3.1.2	Summary of drug-related treatment-emergent adverse events	Safety	16.2.7.1	T_AE1
14.3.2.1	Listing of fatal adverse events	Safety	16.2.7.1	L_AE1_PG
14.3.2.2	Listing of non-fatal serious adverse events	Safety	16.2.7.1	L_AE1_PG
14.3.2.3	Listing of other significant adverse events	Safety	16.2.7.1	L_AE1_PG
14.3.3	Narratives of deaths, other serious and significant adverse events	Safety	-	-
14.3.4.1	Summary of laboratory values outside the normal range by treatment and planned relative time	Safety	16.2.8.1 16.2.8.2 16.2.8.3	T_LB1
14.3.4.2	Summary of laboratory values outside the normal range by treatment	Safety	16.2.8.1 16.2.8.2 16.2.8.3	T_LB3
14.3.5.1	Summary of chemistry laboratory values	Safety	16.4	T_LB2
14.3.5.2	Summary of haematology laboratory values	Safety	16.4	T_LB2
14.3.5.3	Summary of coagulation laboratory values	Safety	16.4	T_LB2
14.3.5.4	Summary of urinalysis results	Safety	16.4	T_UR1

Table	Description	Population	Source Listing	Template (Shells below)
14.3.6.1	Summary of vital signs	Safety	16.4	T_VS1
14.3.6.2	Summary of vital signs outside the normal range by treatment, planned relative time and parameter	Safety	16.2.9.1	T_VS2
14.3.7.1	Summary of ECG values	Safety	16.4	T_EG2
14.3.7.2	Summary of QTcF, QTcB and PR interval values outside the normal range by treatment, planned relative time and category	Safety	16.2.9.3	T_EG3

Figure	Description	Population	Source Listing	Template (Shells below)
14.2	PHARMACOKINETIC DATA			
14.2.1	Individual ASN51 plasma concentration-time plots (linear and semi-log)	PK Analysis	16.2.6.1.1	F_PK1
14.2.2	Individual ASN51 dose-normalised plasma concentration-time plots (linear and semi-log)	PK Analysis	16.2.6.1.1	F_PK1
14.2.3	Mean (+/- SD) ASN51 plasma concentration-time plots (linear and semi-log)	PK Analysis	16.2.6.1.1	F_PK2
14.2.4	Mean (+/- SD) ASN51 dose-normalised plasma concentration-time plots (linear and semi-log)	PK Analysis	16.2.6.1.1	F_PK2

The following abbreviated listings will be produced (templates provided in Section 17.2.3):

Listing	Description	Template (Shells below)
16.2.1	Study dates & disposition of subjects	
16.2.1.1	Listing of study dates	L_SD1_PG
16.2.1.2	Listing of reasons for withdrawal	L_SD2_PG
16.2.2	Protocol deviations	
16.2.2.1	Listing of subjects with inclusion/exclusion criteria deviations	L_DV1_PG
16.2.2.2	Listing of subjects with time deviations	L_TD1_PG

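### SAP 11.2 lets a repeat replace an out-of-range baseline laboratory value but keeps the out-of-range value at every other time, so out-of-range counts tilt towards post-dose worsening to the extent that baselines are repeated

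*SAP*

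**What the plan says.** SAP 11.2 defines baseline for all variables: "Baseline will be considered to be the latest value obtained before study drug administration". For laboratory data it adds that "Out-of-range laboratory tests may be repeated", with no criterion for doing so. Two rules follow:

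- Baseline: "If a test is out of-range at baseline and repeated before dosing, the latest repeat value before dosing will be used as baseline".
- Otherwise: "if a test is out-of-range and repeated at any other time during the study, the out-of-range value (not the repeat value) will be included" in the statistical summaries.

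SAP 11.1 has a further rule: "Data collected at unscheduled time points during the study will not be used in the summaries or data analyses". Such data go to the listings only.

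The displays concerned are in SAP 17.1. Table 14.3.4.1 is the "Summary of laboratory values outside the normal range by treatment and planned relative time", and Table 14.3.4.2 gives the counts by treatment. Tables 14.3.5.1 to 14.3.5.3 summarise values, and their shell (T_LB2) has change-from-baseline columns. Protocol Table 1 and its footnote 19 place post-dose laboratory samples at 72 h in sessions 2 and 3 and at follow-up. Protocol 7.2.1 states that all subjects receive ASN51.

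**The concern.** What triggers replacement at baseline is that the result was out of range, not that the sample was faulty. Some out-of-range results are chance excursions, and a second measurement tends to fall back inside the range. Replacing such results before dosing and keeping them afterwards selects on the outcome on one side of the comparison only. An in-range baseline is never redrawn under this rule, so in expectation replacement can only lower the baseline count.

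Safety is a secondary objective and laboratory tests are a named secondary endpoint. With no placebo or untreated group, a reader of Table 14.3.4.1 judges the post-dose rows largely against the pre-dose row. If that row has been cleaned by repeats, an inert drug can appear to raise the number of abnormal results.

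**Working it through.** The documents give no abnormality rate, repeat rate or test-retest correlation, so there is no planned figure to reproduce. The size has to be shown over a range of assumptions.

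**Inputs from the documents.** The two repeat rules, the optional status of repeats and the table list (SAP 11.2, 17.1); no control group (Protocol 7.2.1); up to 10 subjects (SAP 5).

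**Assumptions, not in the documents.** No drug effect; normally distributed values; a central 95% reference interval, so the single-measurement out-of-range rate is p = 5%; test-retest correlation 0.5 to 0.9; a share r of out-of-range baselines repeated once before dosing; about 30 tests per subject.

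**Formula.** Let q be the probability that the repeat is also out of range, given that the first value was. From the bivariate normal distribution, q = 0.185, 0.331 and 0.593 at correlations 0.5, 0.7 and 0.9. Then:

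- baseline out-of-range rate = p × [1 − r × (1 − q)]
- post-dose out-of-range rate = p

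At correlation 0.7:

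- r = 20%: 5% × [1 − 0.2 × 0.669] = 4.3%; ratio 5.0/4.33 = 1.15
- r = 50%: 5% × [1 − 0.5 × 0.669] = 3.3%; ratio 1.50
- r = 100%: 5% × 0.331 = 1.7%; ratio 3.0

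Baseline rate, with the apparent post/pre ratio in brackets (post-dose is 5.0% throughout):

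| Correlation | r = 0 | r = 20% | r = 50% | r = 100% |
|---|---|---|---|---|
| 0.5 | 5.0% (1.0) | 4.2% (1.19) | 3.0% (1.69) | 0.9% (5.4) |
| 0.7 | 5.0% (1.0) | 4.3% (1.15) | 3.3% (1.50) | 1.7% (3.0) |
| 0.9 | 5.0% (1.0) | 4.6% (1.09) | 4.0% (1.26) | 3.0% (1.69) |

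A simulation of 2,000,000 draws agrees: at correlation 0.7 the baseline rate is 3.34% with half repeated and 1.67% with all repeated, against 5.01% post-dose.

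**In counts.** For 10 subjects × 30 tests = 300 results at correlation 0.7, expect 15 flags at each post-dose time. At baseline expect 15, 13, 10 or 5 flags for r = 0, 20%, 50% or 100%.

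**Mean change from baseline.** If both range limits trigger repeats, the shift is essentially zero. If only high values are repeated, all of them, it is 0.029, 0.018 and 0.006 SD at correlations 0.5, 0.7 and 0.9.

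**Same rule on both sides.** The gap closes whichever rule is chosen: 5.0% against 5.0% if the first value is always used, and 1.7% against 1.7% (correlation 0.7, all repeated) if the repeat is always used.

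**The case against.** The strongest objection is that the bias is not shown to reach the tables. SAP 11.2 says the repeat serves as baseline; it does not say that it fills the pre-dose row of Table 14.3.4.1, whose shell (T_LB1) has no baseline column. SAP 11.1 keeps unscheduled data out of summaries, which could mean that the original scheduled value stays in that row. The shell for Table 14.3.4.2 (T_LB3) has no time column either, although its programming note refers to time points. If the repeat is used only as the reference for change from baseline, the effect is negligible. This stands as an ambiguity. But 11.2 sets the baseline rule directly against one under which "the out-of-range value (not the repeat value) will be included in statistical summaries", and the natural reading of that contrast is that the baseline repeat does enter the summaries. At best, 11.1 and 11.2 conflict.

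Second, the effect depends on repeats that are only permitted. Samples taken on Day -1 of a dosing session leave little time for a repeat before dosing on Day 1, and Protocol 10.6 limits extra blood to 50 mL. Neither rules repeats out, but repeating every out-of-range baseline is a worst case, not a central one.

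Third, the consequences are limited. SAP 4.3 has no hypotheses to test, original values remain visible in the complete listings, and the rule never hides a post-dose abnormality. All of that stands. Over-calling is still not a safe direction: a real signal could be discounted as an artefact of the rule.

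A reader might infer more: that an inert drug is bound to show a several-fold rise, or a large excess of normal-to-abnormal shifts. The documents do not support this. The repeat rate is unknown and could be zero, and no laboratory shift table is planned. Nor is pre-dose versus post-dose the only comparison available: tables are by dose, and post-dose comparisons between dose levels use one rule throughout.

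**Conclusion.** Wrong as written, but minor: it concerns a descriptive safety display. The direction follows from the rule alone. If any out-of-range baselines are repeated and the repeats feed the out-of-range counts, those counts favour apparent post-dose worsening when the drug does nothing. The size cannot be fixed from the documents. With a 95% reference interval and correlation 0.7, the apparent ratio runs from 1.0 (no repeats) through about 1.15 (20%) and 1.5 (50%) to 3.0 (all). With all repeated, it ranges from 5.4 to 1.7 over correlations 0.5 to 0.9. At the low end, 13 flags against 15 would not stand out from chance in a trial of this size (Poisson SD of 15 is √15 ≈ 3.9, before allowing for clustering within subjects). Mean change from baseline is barely affected.

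**What to change.** Replace the two repeat sentences in SAP 11.2 with one rule, for example:

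> For laboratory tests, out-of-range counts and summaries by time point use the first valid scheduled sample at every time point, pre-dose included. A repeat replaces it only if the first sample is documented as invalid (for example haemolysed, or a laboratory error). All repeats are flagged in the listings.

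Two further edits are needed for consistency:

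- Amend the opening baseline definition of 11.2 for laboratory tests, since taking the latest pre-dose value would otherwise bring the repeat back in.
- Reconcile 11.2 with the 11.1 exclusion of unscheduled data, so that it is clear which value fills the pre-dose row of Table 14.3.4.1.

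The cost is a short text change in two sections and a change to the baseline flag in programming; no new data or procedures are needed. The downside is that a few unconfirmed baseline abnormalities will appear in the tables and the baseline SD will be slightly larger.

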11.3 Assessment windows

No assessment windows are defined for this report.

11.4 Vital signs reference ranges

The following vital signs ranges will be used:

Vital Sign	Range
Seated systolic blood pressure	90–140 mm Hg
Seated diastolic blood pressure	50–95 mm Hg
Seated heart rate	45–100 beats/min
Respiration rate	10–16 breaths/min
Tympanic temperature	35.5–37.8°C

12 Study population

12.1 Disposition of subjects

The disposition of all subjects in the safety population will be summarised including: number of subjects randomised; number completing the study, by treatment; and number withdrawn from the study.

All subjects who withdraw or are withdrawn from the study will be listed, by treatment, with the reason for withdrawal.

A listing of analysis populations will be provided.

12.2 Protocol deviations

Before closing the database, data listings will be reviewed to identify any significant deviations and determine whether the data should be excluded from any analysis populations.

Major protocol deviations include subjects who:

- Entered the study even though they did not satisfy the entry criteria.
- Met the criteria for withdrawal from the study but were not withdrawn.
- Received the wrong treatment or incorrect dose.
- Received an excluded concomitant therapy.
- Received investigational product(s) past the expiration date.

In addition, subjects with minor time deviations (measurements taken outside the allowable windows) will be identified. Allowable time windows for pharmacokinetic samples and other procedures are given in HMR Trial Procedures Summary.

12.3 Demographic and baseline characteristics

Demographic and baseline characteristics (eg physical examination, vital signs and ECGs) will be listed and summarised.

Subjects who take concomitant medication will be listed. All non-trial medication will be coded using the latest version of the World Health Organisation (WHO) Drug Global dictionary current at the time of the database lock (version September 2021 or higher).

Medical and surgical history will also be listed.

12.4 Treatment compliance

Dates and times of dosing will be listed.

13 Safety analyses

Summaries and listings of safety data will use the safety population.

13.1 Extent of exposure

The dates and times of treatment dosing will be listed to indicate exposure to the study medication.

13.2 Adverse events

AEs will be coded using the version of the Medical Dictionary for Regulatory Activities (MedDRA) which is current at the time of database lock (version 24.0 or higher).

All AEs will be listed.

The number of subjects with at least one treatment-emergent adverse event (TEAE) per treatment will be tabulated by actual treatment and MedDRA system organ class. A TEAE is defined as an event emerging during treatment (having been absent pre-treatment) or that worsens after treatment¹.

For each of the following, the number of TEAEs and the number of subjects with TEAEs will be summarised by treatment group:

- TEAEs, by system organ class and preferred term
- Drug-related (“related” as recorded by the investigator) TEAEs, by system organ class and preferred term

Subjects with more than one TEAE will be counted only once, at the greatest severity or causality, for each system organ class/preferred term. Multiple TEAEs in a subject will be counted once per system organ class and preferred term. AEs with missing severity and/or causality will be treated as severe and definitely related, respectively.

Summaries will be sorted by system organ class and decreasing total incidence of preferred term.

13.3 Deaths, serious adverse events and other significant adverse events

Deaths and serious adverse events (SAEs) will be listed separately (fatal events separate from non-fatal events). Other significant AEs, as identified by the investigator in the CRF, will be listed separately.

13.4 Adverse events leading to withdrawal from the study

AEs leading to withdrawal will be listed separately.

13.5 Clinical laboratory evaluations

Data from haematology, coagulation, urinalysis and clinical chemistry will be summarised by treatment.

Data from haematology, coagulation and clinical chemistry outside the normal range will be listed separately and summarised.

13.6 Other safety measures

13.6.1 Vital signs

Vital signs evaluation at each planned assessment will be summarised by actual treatment.

Vital signs data outside of the normal range will be listed and summarised.

A separate listing of vital sign findings, classified as clinically significant by the investigator will also be provided.

13.6.2 ECG

QT interval data will be presented using Fridericia's (QTcF) and Bazett (QTcB) corrections.

ECG variables will be summarised by treatment and time point.

QTcF and QTcB values > 450 msec, PR interval shortening < 120 msec, and PR interval prolongation > 220 msec will be listed by treatment and timepoint and summarised. A separate listing of ECG findings classified as abnormal by the investigator will also be provided.

13.6.3 Physical examination

Abnormal physical examination findings will be listed.

13.6.4 Columbia-Suicide Severity Rating Scale (C-SSRS)

Positive C-SSRS data will be listed.

14 Pharmacokinetic analyses

The PK parameters to be derived are given in Appendix : Pharmacokinetic analysis.

PK concentration data and PK parameter data will be summarised using the PK analysis population.

14.1 Pharmacokinetic concentration data

The plasma concentrations and dose-normalised plasma concentrations of ASN51 will be listed and summarised by treatment.

Using actual sample times, linear and semi-logarithmic plasma concentration-time plots will be prepared by treatment and synoptic linear and semi-logarithmic dose-normalised plasma concentration-time plots of ASN51 will be prepared. Both Session 2 and Session 3 profiles will be included on the same plot. The same linear and logarithmic scales will be used for each subject. The linear and semi-logarithmic plots for a given subject will be presented on the same page.

Mean plasma concentration versus time plots will be presented for ASN51 per treatment (synoptic plot) (normal scale and log-linear scale).

Mean dose normalised plasma concentration versus time plots will be presented for ASN51 per treatment (synoptic plot) (normal scale and log-linear scale).

14.2 Pharmacokinetic parameters

The pharmacokinetic parameters of ASN51 will be listed and summarised by treatment.

If there is a quantifiable plasma concentration of the baseline PK sample of session 3, that value will be used in addition for the calculation of the PK parameters for session 2.

15 Pharmacodynamic analyses

15.1 PET analysis data

Start and end date of each PET scan will be listed together with the scan start/stop time and the Dose drawn up, Dose administered, Residual 1, and Residual 2.

[18F]-IMA601 regional total volume of distribution (V_T) at each brain scan will be listed for each session and for change from baseline.

The RO values will be listed for sessions 2 and 3, respectively, together with the plasma concentration of ASN51 at the time of the start of each post-dose PET scan; which will be calculated by log-linear interpolation from the two closest PK data points by subject and treatment.

These concentration data will be transferred to Invicro for the PK-RO analysis. The PK-RO analysis will be provided by Invicro and sent to HMR for the inclusion in the CSR.

16 References

1. International Conference on Harmonization, 1998. Statistical Principles for Clinical Trials – ICH Harmonised Tripartite Guideline. Guidance for Industry, E9, FDA federal register, Vol 63, 1998, p49583. Available at: <http://www.fda.gov/cder/guidance>.
2. International Conference on Harmonization, 1995. Structure and Content of Clinical Study Reports – ICH Harmonised Tripartite Guideline. Guidance for Industry, E3, FDA federal register, Vol 61, 1996, p37320. Available at: <http://www.fda.gov/cder/guidance>.
3. International Conference on Harmonisation, 2005. Clinical Evaluation of QT/QTc Interval Prolongation and Proarrhythmic Potential for Non-Antiarrhythmic Drugs. Concept paper, Guidance for Industry, E14, Center for Drug Evaluation and Research (CDER). Available at: <http://www.fda.gov/cder/guidance/6922fnl.htm>.
4. Julious, SA & Debarnot, CAM (2000) “Why are Pharmacokinetic Data Summarised by Arithmetic Means?”, Journal of Biopharmaceutical Statistics, 10 (1), p55-71

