17. **12-Lead ECG:** During the period of residence, ECGs will be recorded at the timepoints indicated. Assessments will be done at screening visit 1, Day -1 of imaging session 1, and pre-dose on Day 1 in imaging sessions 2 and 3, and at the follow-up visit. Single recordings will be done at all time points. Recordings should be made with subjects in a supine position, after resting for 10 min. Additional unscheduled assessments may be done at the discretion of the Investigator.
18. **PK Sampling:** Plasma samples for assay of the ASN51 will be collected pre-dose and at 0.25, 0.5, 1, 1.5, 2, 3, 4, 6, 8, 12, 16, 24, 36, 48, and 72 h post-dose. Samples scheduled immediately before the PET scan should be taken as close as possible to the planned start of the PET scan samples scheduled for the end of the PET scan should be taken as soon as possible after the PET scan is finished; and samples scheduled during the PET scan should be taken either before or after the PET scan, as close to the scheduled timepoint as possible.
19. Hematology, biochemistry, coagulation, and urinalysis to be taken 72 h post-dose in sessions 2 and 3.
20. **Timing of Assessments:** If more than one assessment is foreseen for a timepoint, PET procedures prevail. All assessments should be staggered in the same order throughout the study with the PK sampling point closest to the scheduled timepoint.

3.0	TABLE OF CONTENTS	
1.0	TITLE PAGE	1
2.0	STUDY SYNOPSIS	4
3.0	TABLE OF CONTENTS	14
4.0	LIST OF ABBREVIATIONS AND DEFINITION OF TERMS	18
5.0	INTRODUCTION AND RATIONALE	21
5.1	Background: O-GlcNAcylation and Protein Aggregation in Neurodegenerative Disease	22
5.2	ASN51 Mechanism of Action and Rationale in Alzheimer's Disease	23
5.3	Nonclinical Studies	25
5.4	Clinical Experience	27
5.5	Summary of Overall Risks and Potential Benefits	27
6.0	OBJECTIVES	28
7.0	INVESTIGATIONAL PLAN	29
7.1	Study Design	29
7.2	Treatment Assignment and Blinding	30
7.2.1	Number of Subjects	30
7.2.2	Method of Assigning Subject Numbers to Treatment Groups	30
7.2.3	Blinding	31
7.2.4	Unblinding	31
7.3	Sites	31
7.4	Study Duration	31
7.5	Study Safety Oversight	31
7.5.1	Safety Review Committee	31
7.5.2	Stopping Criteria Based on Urgent Safety Events	31
7.5.3	Criteria for Dose Level Selection	32
7.6	Subject Discontinuation	32
7.6.1	Removal of Subjects	32
7.6.2	Early Termination Procedure	33

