### **12.11.4 PET Data Reporting**

The PET site [REDACTED] will produce a separate Imaging Analysis Report on the PET scans and the PET scan data. A STDM dataset of the report will be generated by the PET site. The RO values will be listed in both reports for sessions 2 and 3, respectively, together with the plasma concentration of ASN51 at the time of the start of each post-dose PET scan; which will be calculated by log-linear interpolation from the two closest pk data points by subject and treatment (data will come from the sponsor).

These concentration data will be transferred to the PET site for the PK-RO analysis. Three PK-RO analyses will be done: for session 2, for session 3 and for pooled data of session 2 and session 3.

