t_{max}	Time to maximum plasma concentration
V_T	Regional total volume of distribution
WHO	World Health Organisation

2 Signatures

The following persons have read and agreed the content of this Statistical Analysis Plan:

[REDACTED] PhD
Principal Statistician, HMR

[REDACTED] Signature

Nov 22, 2021
Date

[REDACTED] MBBS
Principal Investigator, HMR

[REDACTED] Signature

Nov 24, 2021
Date

[REDACTED] M.D.
[REDACTED] Clinical
Development and Translational
Medicine

[REDACTED]

Nov 17, 2021
Date

3 Introduction

This statistical analysis plan (SAP) is based on the current trial protocol (version 2.0, 19 May 2021). Where statistical methods differ substantially between this SAP and the protocol, that will be identified in this document.

This SAP describes the datasets and the statistical methods to be used for the reporting and analysis of all data collected during the trial except the analysis of the PK-RO which will be done by Invicro.

If a future protocol amendment necessitates a substantial change to the statistical analysis of the trial data, this SAP will be amended accordingly. If, after database lock, additional analyses are required to supplement the planned analyses described in this SAP, those unplanned analyses will not be described in an amended SAP, but they will be identified in the integrated clinical study report (CSR). Any deviations from this SAP will be documented in the CSR.

This SAP has been written in consideration of the following guidelines:

- International Conference on Harmonization (ICH) E9, Guidance for Industry: Statistical Principles for Clinical Trials (ICH E9 1998)¹; and
- ICH E3, Guidance for Industry: Structure and Content of Clinical Study Reports (ICH E3 1995)².

Pharmacokinetic (PK) analysis will be done using WinNonlin v8.3 or higher on a Windows PC. Statistical analysis will be done using SAS® 9.4 or higher on a Windows PC.

4 Study objective(s) and endpoint(s)

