4.2.2 Secondary endpoint(s)

- Treatment-Emergent Adverse Events (TEAEs) and Serious Adverse Events (SAEs) up to follow-up
- Serious Adverse Events (SAEs) up to 4 weeks after last administration
- Laboratory tests
- Vital signs
- ECG
- Physical examination
- Pharmacokinetic (PK): plasma concentration of ASN51 at the time of each post-dose PET scan.
- PK/PD: relationship between ASN51 exposure and receptor occupancy.

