17 ATTACHMENTS

17.1 Table of contents for data display specifications

For overall page layout refer to Appendix B: Sample page .

The numbering in the tables below will take precedence over the numbering in the shells.

The following tables and figures will be produced (templates provided in Section 17.2.1 and 17.2.2):

Table	Description	Population	Source Listing	Template (Shells below)
10.1	Summary of subject disposition	Safety	16.2.1.2 16.2.3.1	T_SD1

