Treatment	Subject	Scan number	{Add. time var.}	Start Date/ Start Time of PET scan	Stop Date/ Stop Time of PET scan	Dose drawn up	Residual 1	Residual 2	Brain Region	V _T (units)	Change from baseline V _T (units)
				[REDACTED]	[REDACTED]						

Template L_PD2

Listing 16.2.xx Listing of receptor occupancy and plasma concentration data of ASN51

Treatment	Subject	Scan number	{Add. time var.}	Start Date/ Start Time of PET scan	Stop Date/ Stop Time of PET scan	Concentration at start of PET scan	Occupancy (%)
				[REDACTED]	[REDACTED]		

Programming notes: Concentration at start of PET scan will be calculated using the closest time before start of PET scan and the closest time after PET scan

Template L_AE1_PG

Listing 16.2.x.xx Listing of all adverse events

Treatment	Subject	System Organ Class* / Preferred Term/ Verbatim Text	Outcome/ Onset Date/Time/ Resolved Date/Time/ Duration	Study Day Started/ Time Since Last Dose	Severity/ Serious/ Withdrawal	Frequency/ Action Taken (1)/ Other Action Taken	Related to Study Drug/ Treatment Emergent?
		Gastrointestinal Disorders / Intestinal Spasm / Enterospasm	Resolved/ [REDACTED]	Day x/ 10d 7h 3m	Mild/ No/ Yes	Intermittent/ Dose not changed/ None	Possibly/ Yes
Treatment 1	[REDACTED]						

(1) Action Taken with Study Treatment

*Coded using MedDRA vXX.X

Programming notes: For the listing of "other significant AEs" include (from ICH E3) AEs leading to withdrawal, AEs leading to dose reduction (including drug withdrawn, interrupted, reduced or similar) and AEs with AEOSE=Y. If AEOSE has not been collected then use "Otherwise significant" in the CRF.

Template L_LB1_PG

Listing 16.2.x.xx Listing of clinical chemistry data outside the normal range

Treatment	Subject	Laboratory test (units)	Planned Relative Time	Date/Time	Study Day	Value	Reference Interval	RI	Clinically Significant?
Treatment 1	[REDACTED]	Alk Phos (U/L)	Time 1	[REDACTED]	-1	64.00	32.0 - 92.0		
			Time 2	[REDACTED]	85	84.00	32.0 - 92.0		
	[REDACTED]	ALT (U/L)	Time 1	[REDACTED]	-1	29.00	10.0 - 40.0		
			Time 2	[REDACTED]	85	70.00	10.0- 40.0	H	Y
				[REDACTED]					

RI for Reference Interval flag;
 H = Above reference interval, L = Below reference interval

Programming notes: Lists only subjects with at least a high or low value

Template L_VS1_PG

Listing 16.2.x.xx Listing of vital signs outside the normal range

Treatment	Subject	Planned Relative Time	Date/Time	Systolic Blood Pressure (mmHg)	Diastolic Blood Pressure (mmHg)	Etc (units)

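### Do SAP 15.1 and the L_PD2 listing note give two different ASN51 concentrations at the start of the PET scan?

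*SAP*

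**What the plan says.** SAP 15.1 lists receptor occupancy beside the ASN51 concentration at the start of each post-dose scan, "which will be calculated by log-linear interpolation from the two closest PK data points by subject and treatment". Protocol 12.11.4 has the same wording: "which will be calculated by log-linear interpolation from the two closest pk data points by subject and treatment". Neither states that the two points must lie on opposite sides of scan start.

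The programming note to template L_PD2 in SAP 17.2.3, the listing that reports this value, reads: "Concentration at start of PET scan will be calculated using the closest time before start of PET scan and the closest time after PET scan". It names no interpolation scale and ties the later point to the scan rather than to its start.

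Two sentences might have settled which text governs, but neither does. SAP 17.1 says "The numbering in the tables below will take precedence over the numbering in the shells", which covers numbering only. SAP section 3 says "Where statistical methods differ substantially between this SAP and the protocol, that will be identified in this document", which covers differences from the protocol, not differences inside the SAP.

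The value is a secondary endpoint in SAP 4.2.2 ("Pharmacokinetic (PK): plasma concentration of ASN51 at the time of each post-dose PET scan"). It is also the only covariate in the protocol's occupancy model, RO = 100 × Cp/(Cp + EC50). On its onward use, SAP 15.1 states: "These concentration data will be transferred to Invicro for the PK-RO analysis".

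**The concern.** Taken literally, the two closest samples can both precede scan start. The calculation is then a short forward extrapolation, whereas the L_PD2 note uses one sample on each side. For a 25 h start at nominal sampling times, the literal rule uses the 16 h and 24 h samples and the note uses 24 h and 36 h. Two programmers could each follow the SAP and produce different numbers.

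At stake would be the reproducibility of a secondary endpoint and of the horizontal axis of the exposure-occupancy fit. If the listing followed one rule and the vendor transfer the other, the clinical study report would list concentrations that do not match the EC50 plot.

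**Working it through.** **Inputs from the documents.** Post-dose sampling times (protocol Table 1, note 18): 0.25, 0.5, 1, 1.5, 2, 3, 4, 6, 8, 12, 16, 24, 36, 48 and 72 h. Scan length is about 90 min (protocol 10.2), and scans may be scheduled up to 48 h post-dose (protocol 7.1). Note 18 adds "Samples scheduled immediately before the PET scan should be taken as close as possible to the planned start of the PET scan" and moves samples due during a scan to before or after it.

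**Assumptions, because the documents give no ASN51 kinetics or assay error.** One-compartment oral profiles with absorption half-life 0.5, 1 or 1.5 h and elimination half-life 10, 20 or 30 h. Scan starts run from 1 to 48 h in steps of 0.05 h (941 starts). The base case has a sample 5 min before each scan and moves in-scan samples to the nearer side.

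**Step 1: how often the samples differ.** At nominal times, the two closest points both precede start s when t(k) < s < [t(k−1) + t(k+1)]/2. That gives 2–2.25, 4–4.5, 8–9, 16–18 and 24–26 h: 0.25 + 0.5 + 1 + 2 + 2 = 5.75 h of 47 h, or 12%. With a sample 5 min before every scan, the pairs differ at about 65% of starts.

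**Step 2: how much the values differ.** Both rules use ln C(s) = (1 − w) ln C(t1) + w ln C(t2), with w = (s − t1)/(t2 − t1). For a 2 h start:

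- Two closest, 1.5 and 1.917 h: w = 0.5/0.417 = 1.20. The pre-scan sample has weight 1.20 and the earlier one −0.20.
- One on each side, 1.917 and 3.583 h: w = 0.083/1.667 = 0.05. The pre-scan sample has weight 0.95.

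The pre-scan sample dominates either way. Largest difference over the nine profiles, in percent of the true concentration:

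| Scan start | Largest difference |
|---|---|
| 1 h | 6.8 |
| 1.05–1.5 h | 3.3 |
| 1.55–3 h | 1.7 |
| 3.05–8 h | 0.7 |
| 24–48 h | about 0 |

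Only about 4% of starts differ by more than 1 point, all at or before 3 h. With the sample 2 or 10 min before the scan, the 2 h figure is about 0.7 or 3.4, and the 1 h figure about 2.6 or 14.6.

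**Step 3: conversion to occupancy.** dRO = RO(1 − RO) × d ln C, which is at most 0.25 occupancy points per 1%. So 1.7% × 0.25 = 0.4 points at 2 h, and 6.8% × 0.25 = 1.7 points at 1 h.

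**Step 4: whether bracketing is more accurate.** Worst bias, two closest against bracketed: +3.5% against −3.4% at 1 h, +0.8% against −2.5% at 1.25 h, +0.6% against −1.0% at 2 h, and under 0.1% for both at 8 h. Bracketing does not reduce bias. It does reduce noise. With independent proportional assay error the multiplier is √(w² + (1 − w)²): at 2 h, √(1.20² + 0.20²) = 1.22 against √(0.05² + 0.95²) = 0.95. Giving all 10 simulated scans these 2 h multipliers moves the standard error of log EC50 from 0.083 (bracketed) to 0.088 (two closest) at 10% assay CV and 5-point occupancy SD. At 15% and 3 points it moves from 0.068 to 0.081.

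**Step 5: the natural reading.** If interpolation means one point on each side, SAP 15.1 and L_PD2 differ only on whether the later sample follows the start or the end of the scan. Once note 18 is applied no sample lies inside the scan, and the two readings pick the same pair at 941 of 941 starts.

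**The case for a change.** The best case for a change is that the words do differ, no precedence rule covers calculations, and a clarification costs only a few sentences and no data. Scan times are adaptive, so early scans cannot be ruled out. Larger gaps can also be constructed. With no extra pre-scan sample, the difference is up to 4.1 points at a 2.2 h start and still 6.8 at 1 h. With a wider range of assumed kinetics, a 2.5 h start and the 3 h sample delayed until after the scan, the rules are up to about 11% apart, or about 2.6 occupancy points.

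The wording point stands: 15.1 could say that the two samples lie on either side of scan start. The larger figures carry less weight. In the 11% case the 3 h sample is due 0.5 h after scan start and 1.0 h before scan end, so note 18 would have it drawn before the scan. Cases without a pre-scan sample sit awkwardly with the PET population (SAP section 9), which requires a PK result immediately before the scan. No 1 h scan is scheduled anywhere; the only stated timing is the baseline scan, about 2 h after dosing water.

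The feared mismatch between listing and fit does not stand. SAP 15.1 describes a single set of concentrations, which is listed and then transferred.

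**Conclusion.** No change to the plan follows. The two passages are loosely worded rather than rival rules: interpolation implies bracketing, and with note 18 observed both lead to the same pair of samples. The SAP identifies no departure from protocol 12.11.4 here, which fits the view that the L_PD2 note was meant to spell out the same calculation.

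If someone did apply 15.1 literally, the effect would be at most about 0.4 occupancy points at a 2 h start and about 1.7 at 1 h, and negligible from 24 h. There would be no loss in bias and a small loss in precision. These sizes rest on the assumed one-compartment profiles and a sample 5 min before the scan; a less prompt sample would enlarge the early-scan figures. The agreement of the two texts under the natural reading needs no kinetic assumption. A competent programmer would bracket scan start anyway, and the EC50 obtained by following the plan would be sound.
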